For survivors of severe COVID-19, overcoming the virus is just the beginning of an uncharted recovery path. As the number of confirmed COVID-19 cases exceeds 27 million globally and 6 million in the US, the number of patients who experience persistent symptoms during recovery is rapidly growing. In COVID-19 patients, common acute symptoms include cough, fever, dyspnea, musculoskeletal symptoms (myalgia, joint pain, fatigue), gastrointestinal symptoms, and anosmia/dysgeusia [1,2]. Clinicians and researchers have focused on the acute phase of COVID-19, but continued monitoring and treating of persistent symptoms is urgently needed. Recent studies [3, 4] assessed persistent symptoms in patients who were discharged from the hospital after recovering from COVID-19. None of the patients had a fever or any of the other signs or symptoms associated with acute illness. Nevertheless, decreased quality of life was observed in 44.1% and fatigue was reported by 53.1% [3] and 71% [4] of patients. Furthermore, persistent fatigue following COVID-19 infection is common and independent of severity of initial infection (hospitalized and non-hospitalized patients) [5]. In addition to the characteristic laboratory findings and lung computed tomography (CT) abnormalities [6], it has been recently reported that patients with COVID-19 also have neurological manifestations [7-9]. Wu et al. [8] found that viral infections have detrimental impacts on neurological functions and can even cause severe neurological damage. Their study showed that coronaviruses (CoV), especially severe acute respiratory syndrome CoV 2 (SARS-CoV-2), exhibited neurotropic properties and may cause neurological diseases with severe fatigue symptoms. Another recent case report has also indicated reduced glucose uptake ([18F]fluorodeoxyglucose (FDG); measured with positron emission tomography (PET)) in diverse brain areas [9], which may contribute to these neurological manifestations. Therefore, there is a critical need to develop inexpensive, effective, and rapid treatments for the persistent fatigue experienced by recovered COVID-19 patients. Without such treatments, these patients will continue to experience fatiguing symptoms that significantly reduce their quality of life. One possible treatment modality is transcranial direct current stimulation (tDCS) [10]. tDCS uses weak currents applied to the scalp to alter the excitability of cortical neurons by changing their spontaneous firing rate. It also has a favorable safety profile and only transient adverse side effects. Studies in patients with neurological disorders have shown that tDCS over the primary motor and/or sensory cortex (M1/S1) consistently and significantly improves fatigue [11-13]. M1 tDCS represents an easy, cost-effective candidate for treating persistent fatigue in recovered COVID-19 patients.

I.5 *Specify your research question(s), study aims or hypotheses (do not indicate "see protocol")*

The objective of this application is to investigate the short- and long-term effects of multiple sessions of 4 mA M1 tDCS on fatigue and brain activity in recovered COVID-19 patients using established measures of perception of fatigue, performance fatigability, and cerebral glucose uptake. Our central hypothesis is that tDCS will improve fatigue short- and long-term, and thus will improve quality of life (QOL) in recovered COVID-19 patients and that these changes will be associated with alterations in brain activity.

Aim 1: Determine the short-term effects of multiple sessions of M1 tDCS on fatigue, and the subsequent influence on QOL, in recovered COVID-19 patients.

Hypothesis 1: Fatigue and QOL will significantly improve immediately after five consecutive sessions of M1 tDCS.

Aim 2: Determine the long-term effects of multiple sessions of tDCS on fatigue and the subsequent influence on QOL, in recovered COVID-19 patients.

Hypothesis 2: The improvements in fatigue and QOL of recovered COVID-19 patients will be present at 3- and 6-week follow-ups.

Aim 3: Determine the association between cerebral glucose uptake and changes in fatigue/QOL measures in recovered COVID-19 patients.

Hypothesis 3: Changes in cerebral FDG uptake will be correlated with improved fatigue and quality of life.

Aim 4: Determine the effects of multiple sessions of tDCS on vascular function (arterial stiffness, endothelial function), baroreflex function, and cognitive function in recovered COVID-19 patients.

Hypothesis 4: Improvements in vascular function (arterial stiffness, endothelial function), baroreflex function, and cognitive function immediately after five consecutive sessions of M1 tDCS, and at 3 weeks and 6 weeks.

I.6 *Background and significance and/or Preliminary studies related to this project. (do not indicate "see protocol")*

As of August 2020, the total number of COVID-19 cases has reached over 5 million nationwide with over 2.5 million recoveries and 160,000 deaths in the US. In Iowa alone, there have been over 47,000 cases, 900 deaths, and 35,000 recoveries. Currently, the immediate effects of COVID-19 are more emphasized than the long-term effects, such as fatigue and deconditioning. Certainly, it is important that healthcare providers monitor and manage the acute effects of COVID-19; but they should also “urgently prepare for . . . the more long-lasting aftershocks of the pandemic” [14].

Even after active COVID-19 cases dissipate, we may experience long-term health consequences for upwards of 12 years [15]. It is highly expected that the needs of COVID-19 survivors will signify a high burden of physical, neuropsychological, and social need following discharge. Specific data concerning the rehabilitation needs of this group is therefore urgently required. Thus, it is not premature to prepare for the time when incidence and death rates have reduced and the number of patients experiencing long-term symptoms that still affect their quality of life are increasing.

Previous coronavirus outbreaks have been associated with long-term symptoms like muscle weakness, pain, fatigue, depression, anxiety, pulmonary function impairment, vocational problems, and reduced quality of life [16-18]. Similarly, COVID-19 may have a lasting impact on physical, cognitive, mental, and social health, even in patients with mild disease presentation [19]. As acute symptoms improve and patients are exiting quarantine, they may be classified as hemodynamically stable and infection-free. Yet, many may still exhibit the physical (i.e., dyspnea, fatigue, weakness, pressure ulcers), cognitive (i.e., delirium), and emotional (i.e., depression) consequences of prolonged bed rest and quarantine, also known as post-intensive care syndrome [19]. These complications may lead to limited mobility, decreased independence in activities of daily living, re-hospitalization, and poor quality of life, all of which may be mitigated by early rehabilitation [20]. These lasting effects are also evidenced by recent studies [3,4] that assessed persistent symptoms in recently discharged COVID-19 patients and reported that decreased quality of life was observed among 44.1% and fatigue was still reported by 53.1% [3] to 71% [4] of patients. Importantly, both hospitalized and non-hospitalized patients showed persistent fatigue after acute COVID-19 infection [5].

Fatigue is “the decrease in physical and/or mental performance that results from changes in central, psychological, and/or peripheral factors” and significantly reduces one’s ability to participate in activities of daily living [21]. Many of the current treatments of fatigue, including pharmaceuticals, are only mildly effective and are often very expensive. Thus, a practical, inexpensive, and effective

adjunct treatment is urgently required. One possible modality that fulfills these requirements is transcranial direct current stimulation (tDCS) [22]. tDCS is a non-invasive means of increasing the excitability of targeted brain regions [9] and has been successfully used for several years in healthy populations [23] and in patients with neurological disorders to treat fatigue [24-27]. Recent studies have shown that tDCS intensities up to 4 mA are safe, tolerable, and do not elicit any serious adverse effects [24,28,29]. Additionally, tDCS can feasibly be delivered outside of a clinic setting [30], which may be of particular importance during a pandemic.

I.7

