- *Physician services or services provided by non-physicians who are credentialed to bill (ARNPs, Physician Assistants, etc.)*

- Yes

V.25.b *Will there be any procedures or services that may happen as part of a subject's regular medical care and as part of the study?*

No

V.25.c *Will any study equipment or devices be supplied by a study sponsor?*

No

V.25.e *Is there or will there be an internal budget for this study?*

Yes

V.25.f *Is there or will there be an external budget for this study?*

No

V.26 *The study involves Department of Nursing Services and Patient Care nursing, nursing resources or evaluates nursing practices at UI Health Care.*

No

VI. Subjects

VI.1 *How many adult subjects do you expect to consent or enroll for this project?*
150

VI.2 *What is the age of the youngest adult subject?*
18.0

VI.3 *What is the age of the oldest adult subject?*
80.0

VI.4 *What is the percentage of adult male subjects?*
50

VI.5 *What is the percentage of adult female subjects?*
50

VI.6 *How many minor subjects do you expect to consent or enroll for this project?*
0

VI.13 *Describe EACH of your subject populations*

- *Include description of any control group(s)*
- *Specify the Inclusion/Exclusion criteria for EACH group*

Fifty post-acute COVID-19 men and women with enduring fatigue will be recruited into one of two groups (tDCS or sham, n = 25 in each group), 50 post-acute COVID-19 men and women without enduring fatigue will be recruited into one of two groups (tDCS or sham, n = 25 in each group), and 50 subjects with no history of a COVID-19 diagnosis (controls) will be recruited into one of two groups (tDCS or sham, n = 25 in each group). For the COVID-19 subjects (fatigue and without fatigue), only those that are discharged from the UIHC COVID-19 inpatient clinic and/or that meet the CDC guidelines for discontinuing home isolation (i.e., fever-free for at least 24 hours, all symptoms improved after 10 days) will initially be

considered as long as they meet the rest of the following criteria:

Inclusion criteria (COVID-19 fatigue subjects):

- 18–80 yrs.
- Previous positive COVID-19 test
- >30 days since positive COVID-19 diagnosis
- Meet CDC guidelines (<https://www.cdc.gov/coronavirus/2019-ncov/hcp/duration-isolation.html>) for discontinuation of home isolation
- Meet the criteria for fatigue, based on the Chalder Fatigue Scale CFQ-11 case definition of fatigue

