The data that will be shared with the Medical University of South Carolina (MUSC) will be de-identified, age, race and ethnicity will be reported as required by NIH (see attached template that will be requested for reporting purposes) as part of a final report to MUSC.

X.7

Does your study meet the NIH criteria for a Certificate of Confidentiality or will you be applying for Certificate of Confidentiality?

No

XI. Data Analysis

XI.1

Describe the analysis methods you will use, including, if applicable, the variables you will analyze

The generalized estimating equation (GEE) framework will be utilized to assess changes over time in fatigue and quality of life measures. An interaction term between time and treatment will allow us to test the within- and between-treatment differences over all time points. Using histograms, variable distributions will be assessed to decide which link function to specify when modeling each outcome. To account for the inherent correlation that occurs in repeated measures data, we will cluster on subject ID. In addition to

examining the unadjusted relationship between the time-treatment interaction and each outcome, we will consider the addition of control variables, which will reduce the likelihood of unaccounted confounders. The control variables being considered for inclusion in the adjusted models are age, sex, and disease duration. For each outcome, models will be fit for all possible combinations of control variables. The predictor set that yields the smallest Akaike information criterion (AIC) will be considered the optimal control variable set to adjust associations between the main predictor and the outcomes. Statistical significance will be assessed at the $\alpha = 0.05$ level.

XI.2

Provide the rationale or power analysis to support the number of subjects proposed to complete this study.

The sample size calculation was based on the Fatigue Severity Scale data from our own preliminary data that assessed the effects of multiple sessions of 4 mA tDCS on fatigue in people with multiple sclerosis. The effect size of this difference = 0.91 (Cohen's d). With alpha fixed at 0.05, we would need 20 total subjects in each group (tDCS and SHAM; details below) to achieve 80% power in a two-tailed independent samples test. Therefore, to account for 20% data and subject attrition, we will recruit 25 subjects per group (150 total).

XII. Future Research

XII.1

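### Hypotheses 1, 2 and 4 name no comparator, and XI.1 plans both within-arm and between-arm tests of fatigue and QOL without saying which decides

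*Combined protocol and SAP*

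**What the plan says.** Section I.5 sets out the claims. The central statement is "Our central hypothesis is that tDCS will improve fatigue short- and long-term". The specific hypotheses follow the same pattern:

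- "Hypothesis 1: Fatigue and QOL will significantly improve immediately after five consecutive sessions of M1 tDCS"
- "Hypothesis 2: The improvements in fatigue and QOL of recovered COVID-19 patients will be present at 3- and 6-week follow-ups"
- "Hypothesis 4: Improvements in vascular function (arterial stiffness, endothelial function), baroreflex function, and cognitive function immediately after five consecutive sessions of M1 tDCS", and again at 3 and 6 weeks.

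None of these mentions sham or a difference between groups.

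Section VII.E.2 describes a randomised, double-blind parallel trial with a sham control. Section XI.1 fits GEE models to fatigue and QOL measures with this contrast: "An interaction term between time and treatment will allow us to test the within- and between-treatment differences over all time points". Significance is judged at 0.05. No primary contrast or time point is named. The vascular, baroreflex and cognitive outcomes of Hypothesis 4 are not mentioned in XI.1.

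Section XI.2 takes an effect size of 0.91 and finds 20 subjects per group enough "to achieve 80% power in a two-tailed independent samples test", raised to 25 for 20% attrition. Section VII.B.11 confirms that no separate written protocol exists, so the deciding contrast cannot be assumed to be stated in one.

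**The concern.** The design and the sample size serve one question: does tDCS do better than sham? The hypotheses as worded ask another: do outcomes get better after tDCS? A significant before-after change in the tDCS arm satisfies Hypothesis 1 literally, whatever happens under sham. Because XI.1 plans both kinds of test with no rule for choosing, that choice can be left until the results are known.

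Some improvement common to both arms is plausible here. The fatigue group is selected for meeting a fatigue case definition (VI.13). Fatigue is self-rated on the FAS and FSS (VII.E.4). Entry is allowed ">30 days since positive COVID-19 diagnosis", and participation lasts about seven weeks (VII.E.6). Regression to the mean, placebo response and continuing recovery would all move both arms the same way. At stake is a report that tDCS improves fatigue and QOL when it adds nothing to sham.

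**Working it through.** **1. The plan's own figure.** Inputs from XI.2: d = 0.91, two-sided alpha 0.05, power 80%, attrition 20%.

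- Normal approximation: n = 2(1.960 + 0.842)² / 0.91² = 18.96, so 19 per group.
- Noncentral t, two-sample test: n = 19.96, so 20 per group. Power at 20 is 0.801.
- A one-sided test would need only 16 (15.65), which does not match the plan.
- Attrition: 20 / (1 − 0.20) = 25.

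The stated 20 evaluable and 25 recruited per group reproduce as a two-sided between-arm calculation.

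**2. What the XI.1 model contains.** For one follow-up time and an identity link, write the mean as b0 + b1·A + b2·T + b3·A·T, with A = 1 for tDCS and T = 1 at follow-up.

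- Change within sham: b2.
- Change within tDCS: b2 + b3.
- Between-arm difference in change: b3.

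Any improvement shared by the arms sits in b2. A within-tDCS test asks whether b2 + b3 = 0, so it can reject when b3 = 0. Only the test of b3 isolates tDCS from sham.

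**3. Size of the problem if the within-arm test decides.** The documents give no figure for improvement under sham, so it is assumed. Let δ be the mean change common to both arms in SDs of change, with b3 = 0. The paired t statistic follows a noncentral t with n − 1 degrees of freedom and noncentrality δ√n. The probability of a significant improvement is P(T > t at 0.975), with critical value 2.093 for n = 20 and 2.064 for n = 25.

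| δ (assumed) | δ√20 | Within-tDCS, n = 20 | Within-tDCS, n = 25 | Between-arm, two-sided |
|---|---|---|---|---|
| 0.2 | 0.894 | 0.133 | 0.159 | 0.05 |
| 0.3 | 1.342 | 0.246 | 0.302 | 0.05 |
| 0.5 | 2.236 | 0.564 | 0.670 | 0.05 |
| 0.8 | 3.578 | 0.924 | 0.970 | 0.05 |

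The between-arm column does not depend on δ, because the expected difference is δ − δ = 0; half of its 5%, or 2.5%, favours tDCS. A simulation of 40,000 trials at δ = 0.3, 0.5 and 0.8 with 20 per arm gave within-arm rates of 0.247, 0.566 and 0.923, and two-sided between-arm rates of 0.051, 0.050 and 0.050.

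**4. Sensitivity to the unit.** If the common improvement is expressed in SDs of the raw score, d, then δ = d / √(2(1 − ρ)), where ρ is the correlation between baseline and follow-up. For d = 0.5 and ρ = 0.3, 0.5 or 0.7, δ is 0.423, 0.5 or 0.645, and the within-tDCS rate at n = 20 is 0.434, 0.564 or 0.782.

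**The case against.** The strongest reply is that the rest of the plan is between-arm. The aims ask about effects of tDCS, which is a causal question. The trial randomises to sham, and its only sample-size calculation compares the arms, which would be pointless if a within-arm change were the criterion. The sentence in XI.1 that plans within-arm tests plans between-arm tests too. XI.1 also treats the time-by-treatment interaction as the relationship of interest and later speaks of a main predictor, which is most naturally that interaction.

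Most of this stands. A reader might infer that the trial has no sham comparison, or that XI.1 plans only within-arm tests; the documents support neither. The main-predictor wording does not settle the matter, however, because XI.1 says the same interaction term serves both kinds of test.

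Three further limits are fair:

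- XI.1 names only fatigue and QOL, so it does not plan within-arm tests of the Hypothesis 4 outcomes. For those, the defect is the missing comparator and the absence of any stated analysis.
- The case for common improvement is weaker in places. Mass-email recruits had their positive test at least 3 months earlier (VII.D.29), Hypothesis 1 covers only Day 1 to Day 5, and selection uses the Chalder scale while the Day 1 battery lists the FAS and FSS. None of this removes placebo response or all regression to the mean.
- The illustration uses a paired t-test, while the plan uses GEE.

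**Conclusion.** The point holds as a gap in the decision rule. The central hypothesis and Hypotheses 1, 2 and 4 name no comparator. For fatigue and QOL, XI.1 plans both contrasts at 0.05 and ranks neither. Improvement common to both arms could therefore be presented as confirming Hypotheses 1 and 2.

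The rates of 13% to 92% (20 completers) rest on three assumptions: no tDCS effect over sham, a common improvement of 0.2 to 0.8 SD of change, and reliance on the within-arm test. A reader might take them as the plan's false-positive rate. They are not: the documents give no sham response and do not say that the within-arm test will decide. They show what relying on that test would cost, against 5% for the between-arm test.

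**What to change.** - In I.5, reword Hypotheses 1, 2 and 4 as greater improvement with tDCS than with sham from Day 1 to Day 5 and to the 3- and 6-week follow-ups, and bring the central hypothesis into line.
- In XI.1, state that the treatment-by-time contrast, meaning the between-arm difference in change from baseline, decides these hypotheses.
- Extend that analysis explicitly to the vascular, baroreflex and cognitive outcomes of Hypothesis 4.
- Report within-arm changes as descriptive estimates that do not support an efficacy conclusion.

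This is a change of wording. It needs no new data or visits, and no resizing, since the 20 evaluable (25 recruited) per group already rests on a between-arm test. The only thing given up is the option of claiming success on within-arm change.

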V. Other Committee Review

V.1 **Does this project involve any substance ingested, injected, or applied to the body?**

- **Do not answer yes, if the involvement includes a device, wire, or instrument**
- Yes

V.1.a **What is/are the substance(s):**
[18F]flurodeoxyglucose (18F-FDG)

V.1.b **Are any of these substances defined as a Schedule I - V Controlled Substance?**
No

V.2 **Are any contrast agents used for any purpose in this study?**
No

V.4 **Are all drugs or substances in this study being used within the FDA approved population (i.e., children, adults)?**
Yes

V.5 **Are all drugs or substances in this study being used within the FDA approved indication (i.e., disease, condition)?**
Yes

V.6 **Are all drugs or substances in this study being used within the FDA approved dose?**
Yes

V.7 **Are all drugs or substances in this study being used within the FDA approved route of administration?**
Yes

V.9 **Will any subject be asked to undergo a diagnostic radiation procedure (including radiographic, nuclear medicine, DEXA)?**
Yes

V.10 **Are all diagnostic radiation procedures routine, standard, clinical procedures?**
Yes

V.11 **Will all subjects who receive the diagnostic radiation procedure(s) require the exact same procedure for clinical purposes?**
No

V.14 **Will any subject be asked to undergo a radiation therapy procedure (including external beam therapy, brachytherapy, or nuclear medicine therapy)?**
No

V.20 **Does this project involve the deliberate transfer of recombinant or synthetic nucleic acid molecules, or DNA or RNA derived from recombinant or synthetic nucleic acid molecules, into one or more human research participant?**
No

V.21 **Will any portion of this project be conducted in the CRU, or does it use any CRU resources?**
No

V.22 **Will this project use:**

- *any resource/patients of the Holden Comprehensive Cancer Center*
- *involve treatment, detection, supportive care, or prevention of cancer*

- No

V.25.a *Will the study involve any of the following activity at UI Health Care, even if subjects or their insurance will not be billed for the item or service, and regardless of the study funding source (including studies with departmental or no funding)?*

- *Procedures, tests, examinations, hospitalizations, use of Pathology services, use of clinic facilities or clinical equipment, or any patient care services, including services conducted in the Clinical Research Unit; or*
- *Physician services or services provided by non-physicians who are credentialed to bill (ARNPs, Physician Assistants, etc.)*

- Yes

V.25.b *Will there be any procedures or services that may happen as part of a subject's regular medical care and as part of the study?*

No

V.25.c *Will any study equipment or devices be supplied by a study sponsor?*

No

V.25.e *Is there or will there be an internal budget for this study?*

Yes

V.25.f *Is there or will there be an external budget for this study?*

No

V.26 *The study involves Department of Nursing Services and Patient Care nursing, nursing resources or evaluates nursing practices at UI Health Care.*

No

VI. Subjects

VI.1 *How many adult subjects do you expect to consent or enroll for this project?*
150

VI.2 *What is the age of the youngest adult subject?*
18.0

VI.3 *What is the age of the oldest adult subject?*
80.0

VI.4 *What is the percentage of adult male subjects?*
50

VI.5 *What is the percentage of adult female subjects?*
50

VI.6 *How many minor subjects do you expect to consent or enroll for this project?*
0

VI.13 *Describe EACH of your subject populations*

- *Include description of any control group(s)*
- *Specify the Inclusion/Exclusion criteria for EACH group*

Fifty post-acute COVID-19 men and women with enduring fatigue will be recruited into one of two groups (tDCS or sham, n = 25 in each group), 50 post-acute COVID-19 men and women without enduring fatigue will be recruited into one of two groups (tDCS or sham, n = 25 in each group), and 50 subjects with no history of a COVID-19 diagnosis (controls) will be recruited into one of two groups (tDCS or sham, n = 25 in each group). For the COVID-19 subjects (fatigue and without fatigue), only those that are discharged from the UIHC COVID-19 inpatient clinic and/or that meet the CDC guidelines for discontinuing home isolation (i.e., fever-free for at least 24 hours, all symptoms improved after 10 days) will initially be

considered as long as they meet the rest of the following criteria:

Inclusion criteria (COVID-19 fatigue subjects):

- 18–80 yrs.
- Previous positive COVID-19 test
- >30 days since positive COVID-19 diagnosis
- Meet CDC guidelines (<https://www.cdc.gov/coronavirus/2019-ncov/hcp/duration-isolation.html>) for discontinuation of home isolation
- Meet the criteria for fatigue, based on the Chalder Fatigue Scale CFQ-11 case definition of fatigue
- Healthy enough to complete the protocol based, on information obtained from a clinical exam and past medical history, such as cardiovascular disease.
- Comprehension of the protocol, as indicated by an ability to respond to questions about the study after reading the consent form.
- Able to use and be contacted by telephone
- Able to speak, read, and understand English, and complete questionnaires in English

Exclusion criteria

- Medical diagnosis or condition that is considered to be an absolute or relative contraindication to participating in exercise training, such as major renal, pulmonary, hepatic, cardiac, gastrointestinal, HIV, cancer (other than treated basal cell cancer), or neurological disorders
- History/presence of secondary conditions such as seizure disorders (or on medications known to lower seizure threshold), hydrocephalus, diabetes mellitus, or claustrophobia
- Alcohol dependence or abuse (>2 drinks/day), or present history of drug abuse (last six months)
- History of significant traumatic brain injury or hydrocephalus
- Pregnancy

Inclusion criteria (COVID-19 non-fatigue subjects):

- 18–80 yrs.
- Previous positive COVID-19 test
- >30 days since positive COVID-19 diagnosis
- Meet CDC guidelines (<https://www.cdc.gov/coronavirus/2019-ncov/hcp/duration-isolation.html>) for discontinuation of home isolation
- Do not meet the criteria for fatigue, based on the Chalder Fatigue Scale CFQ-11 case definition of fatigue
- Healthy enough to complete the protocol based, on information obtained from a clinical exam and past medical history, such as cardiovascular disease.
- Comprehension of the protocol, as indicated by an ability to respond to questions about the study after reading the consent form.
- Able to use and be contacted by telephone
- Able to speak, read, and understand English, and complete questionnaires in English

Exclusion criteria

- Medical diagnosis or condition that is considered to be an absolute or relative contraindication to participating in exercise training, such as major renal, pulmonary, hepatic, cardiac, gastrointestinal, HIV, cancer (other than treated basal cell cancer), or neurological disorders
- History/presence of secondary conditions such as seizure disorders (or on medications known to lower seizure threshold), hydrocephalus, diabetes mellitus, or claustrophobia
- Alcohol dependence or abuse (>2 drinks/day), or present history of drug abuse (last six months)
- History of significant traumatic brain injury or hydrocephalus
- Pregnancy

Inclusion criteria (control subjects):

- 18–80 yrs.
- Healthy enough to complete the protocol based, on information obtained from a clinical exam and past medical history, such as cardiovascular disease.
- Comprehension of the protocol, as indicated by an ability to respond to questions about the study after reading the consent form.
- Able to use and be contacted by telephone
- Able to speak, read, and understand English, and complete questionnaires in English

Exclusion criteria

- Medical diagnosis or condition that is considered to be an absolute or relative contraindication to participating in exercise training, such as major renal, pulmonary, hepatic, cardiac, gastrointestinal, HIV, cancer (other than treated basal cell cancer), or neurological disorders
- History/presence of secondary conditions such as seizure disorders (or on medications known to lower seizure threshold), hydrocephalus, diabetes mellitus, or claustrophobia
- Alcohol dependence or abuse (>2 drinks/day), or present history of drug abuse (last six months)
- History of significant traumatic brain injury or hydrocephalus
- Pregnancy

VI.14

Provide an estimate of the total number of subjects that would be eligible for inclusion in each of your study populations (include your control population if applicable)

A patient search was completed using TriNetX. On 2 Sept 2020, there were 42,530 registered COVID-19 patients at UIHC. Given that previous research has indicated that 53% - 71% of recovered patients still experience persistent fatigue, our potential subject pool would consist of 22,500+ people, of which we will only seek to recruit 100. The control subjects will likely come from the student and employee pools from UI and UIHC. Our experience indicates that recruiting 50 subjects will not result in any undue burdens.

VI.15

Describe how you will have access to each of your study populations in sufficient number to meet your recruitment goals.

Prospective participants will be recruited from the University of Iowa Hospitals and Clinics, Iowa City, IA, via advertisements throughout the university campus and community, mass email to the university staff, faculty and alumni (>35,000 recipients), and from the 'volunteer research' link on the clinical trials webpage on the University of Iowa Hospitals and Clinics website (<https://uihc.org/clinicaltrials/>). Other main recruiting tools will include advertisements in local newspapers (Iowa City Press Citizen, Cedar Rapids Gazette) and Noon News publications in the University of Iowa Hospitals & Clinics daily newsletter, which is available to the public and patients at various locations in the hospital. Drs. [name], [name], and [name] will also assess interest and provide referrals from visitors/patients in their clinics.

VI.16

Do you plan to recruit/enroll non-English speaking people?

No

VI.18

Do you propose to enroll any of the following in this study as subjects?

- *Employee of the PI or employee of a research team member*
- *Individual supervised by PI or supervised by member of research team*
- *Individual subordinate to the PI or subordinate to any member of the research team*
- *Student or trainee under the direction of the PI or under the direction of a member of the research team*

- No

VI.20

Will subjects provide any information about their relatives?

No

VI.23

Will anyone (other than the subject) provide you with information about the subject (e.g. proxy interviews)?

No

VI.26

Is this project about pregnant women?

No

VI.27

Will this project involve fetuses?

No

VI.28

Does this project involve adult subjects who may be incompetent or have limited decision-making capacity on initial enrollment into the study?

No

VI.32

Does this project involve subjects whose capacity to consent may change over the course of the study?

No

VI.37

Does this project involve prisoners as subjects?

No

VII.A. Project Description (A)

VII.A.1

Where will project procedures take place (check all that apply)?

- Other UI campus site - Department of Health and Human Physiology, Integrative Neurophysiology Laboratory; Pappajohn Biomedical Discovery Building (PBDB);
- UIHC - Department of Neurology; Department of Internal Medicine (COVID-19 Home Treatment Clinic); PET Imaging Center; Iowa Translational Vascular Physiology Lab ([name] PI) in C204 GH

VII.A.2

Is this project also being conducted by other researchers at their own sites (e.g. a multi-site collaborative project)?

Yes

VII.A.3

What is the UI site's role(s) for this project (check all that apply)?

- Clinical/participating site

VII.A.10

What are collaborating site roles for this project?

- Other - MUSC is the pilot grant organization for the study.

VII.B. Project Description (B)

VII.B.1.

Does this project involve any of the following (Check all that apply):

-

Interventional – Includes Clinical (or Treatment) trial, Physiology intervention/study, Behavioral intervention/study, Diagnostic Trial.

-

Clinical (or Treatment) trial – A prospective biomedical or behavioral research study of new treatments, new drug or combinations of drugs, new devices, or new approaches to surgery or radiation therapy. (NIH and [ClinicalTrials.gov](#) & [FDA](#))

Physiology intervention/study – A pharmacologic or measurement study aimed at understanding basic mechanisms of disease and/or of normal human physiology, often without any therapeutic intent (though a clinical trial could include such components, often labeled as “translational” or “basic science” aims.) Measurements in such studies could include, but are not limited to, a blood draw, EKG, EEG, MRI, auditory or sensory testing, checking vital signs, DEXA scans, eye tracking, specimen collection, exercise, fasting, special diets, etc.

Behavioral intervention/study – May be used to refer to studies of individual or group behavior. This option does not include drugs, biologics, or devices but could include psychotherapy, lifestyle counseling, behavior modification, etc.

Diagnostic trial – Protocol designed to evaluate one or more interventions aimed at identifying a disease or health condition ([ClinicalTrials.gov](#) & [FDA](#))

Observational

Expanded Access – A process regulated by the Food and Drug Administration (FDA) that allows manufacturers to provide investigational new drugs to patients with serious diseases or conditions who cannot participate in a clinical trial. Examples of expanded access include non-protocol access to experimental treatments, including protocol exception, single-patient IND, treatment IND, compassionate use, emergency use, continued access to investigational drug, and parallel track ([ClinicalTrials.gov](#) & [FDA](#)).

Registry – The collection and maintenance of data (not including biologic samples) in which: (1) the individuals in the registry have a common or related condition(s), and/or (2) the individuals in the registry are interested in being contacted for future studies by investigators other than those listed in Section II of this project. ([UI Guide](#))

Repository – The collection, storage, and distribution of human biologic samples and/or data materials for research purposes. Repository activities involve three components: (i) the collection of data and/or specimens such as blood, tissue, saliva, etc.; (ii) the storage of data or specimens, and data management function; and (iii) the sharing of data/specimens with recipient investigators other than the original investigators. (paraphrased from [OHRP](#))

Other

VII.B.1.a Does this project involve any of the following (Check all that apply):

Phase I trials – include initial studies to determine the metabolism and pharmacologic actions of drugs in humans, the side effects associated with increasing doses, and to gain early evidence of effectiveness; may include healthy participants and/or patients ([ClinicalTrials.gov](#) & [FDA](#))

Phase II trials – include controlled clinical studies conducted to evaluate the effectiveness of the drug for a particular indication or indications in patients with the

disease or condition under study and to determine the common short-term side effects and risks([ClinicalTrials.gov](#) & [FDA](#))

-

Phase III trials – include expanded controlled and uncontrolled trials after preliminary evidence suggesting effectiveness of the drug has been obtained, and are intended to gather additional information to evaluate the overall benefit-risk relationship of the drug and provide an adequate basis for physician labeling([ClinicalTrials.gov](#) & [FDA](#))

-

Phase IV trials – studies of FDA-approved drugs to delineate additional information including the drug's risks, benefits, and optimal use([ClinicalTrials.gov](#) & [FDA](#))

VII.B.1.c *What is the last date the final subject/participant will undergo an intervention (i.e. the last study visit by any subject) as required by the protocol?*
05/26/2023

VII.B.2 *Does this project involve a drug washout (asking subject to stop taking any drugs s/he is currently taking)?*
No

